6.4 Analysis of the CARTOFINDER™ Baseline Map

After completion of the CARTOFINDER™ baseline mapping procedure, the CARTOFINDER™ maps will be

processed and analyzed for the presences of ablation targets including FI/RAPs by the treating/ablating investigator who has been trained by Biosense Webster personnel knowledgeable in analyzing CF maps and the operation of the CARTOFINDER™ system.

Ablation Targets (FI/RAP) identification:

- Identify areas with ablation targets including focal impulse (FI) or repetitive activation patterns (RAPs)
 - If an ablation target is identified, the subject will receive CFGA followed by PVI
 - If no CF ablation target is identified, the subject will be treated per standard of care and exits the study after 7 day follow up.

No RF ablation should occur prior to analysis of the CARTOFINDER™ Maps.

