An interim analysis will be performed when 20 evaluable subjects are reached, who have the RHYTHMFINDER™ 192 Catheter inserted and CARTOFINDER guided ablation performed. The interim analysis is not proposed in the protocol. Details of the analysis will be described in the section 10.5.

2 Treatment Assignment

All enrolled patients will undergo the CARTOFINDER™ mapping procedure to identify the ablation targets.

The CARTOFINDER™ 4D LAT Algorithm provides automatic analysis of multiple simultaneous ECG signals recorded by a multi-electrode catheter and leads to the generation of a CARTOFINDER™ Map. The CARTOFINDER™ Map may facilitate the identification of ablation targets including Repetitive Activation Patterns (RAPs) or Focal Impulses (FI) or other ablation targets.

Subjects displaying ablation targets on the CARTOFINDER™ (CF) map will undergo CARTOFINDER™ Guided Ablation (CFGa) and subsequently the PVI (WACA) ablation. Subjects not displaying ablation targets on CARTOFINDER™ will be treated per investigator's standard of care and be followed up 7 days after the ablation procedure.

3 Randomization and Blinding Procedures

Not Applicable.

4 Interval Windows

After the index ablation procedure, subjects will enter a 3-Month Blanking Period (Day 0-90) and then a 9-Month Evaluation Period (Day 91-365). During evaluation period, subjects will undergo follow up visits at predefined intervals (at 7 days, 3, 6, and 12 months post the index procedure) to receive study assessments. Subjects will complete the RAPID-AF study after completing the 12-month follow up visit.

| | Screening / Baseline | Ablation Procedure ¹ | Discharge | 7 Days +/- 2 day | 3 Month +/- 1 wks. | 6 Month +/- 2 wks. | 12 Month +/- 4 wks. |
|--|----------------------|---------------------------------|-----------|------------------|--------------------|--------------------|---------------------|
| Informed consent ¹ | X | | | | | | |
| Inclusion & exclusion criteria | X | | | | | | |
| Demographics | X | | | | | | |
| Medical assessment | X [history] | | | X | X | X | X |
| Arrhythmias | X [history] | | X | X | X | X | X |
| ECG (12 lead and CL measurement) | X | | X | | X | X | X |
| NYHA/CHADS ₂ -VASC ₂ score | X | | | | | | |
| Pregnancy Test ² | X | | | | | | |
| Assessment LA Thrombus ³ | | X | | | | | |
| TTE ⁴ | X | | | | | | |
| Ablation assessments | | X | | | | | |
| Arrhythmia Monitoring (Holter) ⁸ | | | | | X | X | X |
| Device Deficiency | | X | | | | | |

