5.1 Study Endpoint(s)

Effectiveness

- Acute success defined as: Rate of conversion of Atrial Fibrillation to Normal Sinus Rhythm or Atrial Tachycardia, after CFGA and PVI (without cardioversion)
- Procedural success defined as: Conversion of Atrial Fibrillation to Normal Sinus Rhythm or Atrial Tachycardia after overall ablation procedure, with or without the need for cardioversion
- Rate of conversion of Atrial Fibrillation to Normal Sinus Rhythm or Atrial Tachycardia, after CFGA only (before PVI and without cardioversion)
- Freedom from documented symptomatic AF/AT/AFL recurrence (episodes ≥ 30 seconds on an arrhythmia monitoring device) post the 3-month blanking period through the 12-month follow up.

- Incidence of PVI (confirmed entrance block) after adenosine/isoproterenol challenge
- Change of intra-cycle length from pre-CFGA to post-CFGA and post-PVI

Safety

- Incidence of early-onset Primary Adverse Events
- Incidence of study device and procedural related SAEs during follow-up period (12M)
- Incidence of all SAEs during follow-up period (12M)
- Incidence of study device and procedure related adverse events

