5.2 Other Endpoints

- Investigational Device Performance
 - Number of identified CF ablation targets
 - Max number of active RF 192 electrodes during initial mapping procedure
- AAD use post the 3-month blanking period
- Incidence of repeat ablation procedures for AF post the 3-month blanking period
- Procedural data
 - All target sites for RF lesion application
 - Location of ablation targets
 - Number of RF applications per target
 - Total RF duration per application
 - RF ablation parameters (including but not limited to: power, contact force, impedance, flow rate, temperature)
 - Total fluoroscopy time and dose
 - Total procedure, mapping and ablation time

6 Levels of Significance

No formal statistical hypothesis and inferential statistics will be formulated and performed. Two-sided 95% confidence intervals will be constructed for the effectiveness and safety endpoints.

7 Analysis Sets

The following analyses populations will be used to complete the analyses of the data:

- **Safety Subject Population (SP)**: The safety subject population will include all enrolled subjects who have the RHYTHMFINDER™ 192 Catheter inserted, regardless if CARTOFINDER guided ablation was performed.
- **Evaluable Subject Population (EP)**: The evaluable subject population will include all enrolled subjects who have the RHYTHMFINDER™ 192 Catheter inserted and where CARTOFINDER guided ablation was performed.

- **Effectiveness Subject Population (Efp):** The effectiveness subject population will include all Evaluable Subjects who meet the study eligibility criteria. Efp was not included in the protocol but added in the SAP.

8 Sample Size Justification

This is a feasibility study of safety and effectiveness in which the sample size of the clinical investigation is intended to provide preliminary estimates of these two aspects. Enrollment in the clinical investigation will be approximately 40-70 evaluable subjects.

9 Data Monitoring Committee (DMC)

No Data Monitoring Committee will be constituted for the study.

10 Analyses to be Conducted

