10.4 Endpoint Analyses

Descriptive statistics and two-sided 95% confidence intervals will be presented for the effectiveness and safety endpoints. No formal statistical hypothesis and inferential statistics will be formulated and performed. Analyses of all endpoints will be performed in the proposed analysis populations excluding the subjects with missing outcomes.

- **Safety**

The incidence of early-onset Primary Adverse Events is the percentage of patients with at least one primary adverse event with onset on Day 0 through Day 7 except for pulmonary vein (PV) stenosis and atrio-esophageal fistula that could occur greater than one week (7 days) post-procedure . The number of primary adverse events and the number of subjects experiencing primary adverse events will be reported.

Incidence of (S)AEs during the 12 month follow-up will be reported as the number of (S)AEs and the number of subjects experiencing (S)AEs. The number and percentage of subjects with (S)AEs will be summarized overall and by AE type, seriousness, severity, relationship to device and procedure, anticipated or not and outcome. Listing of (S)AEs will also be provided.

The SP will be used as the analysis population.

- **Effectiveness**

Effectiveness outcomes includes

1. **Acute Success**: Rate of conversion of Atrial Fibrillation to Normal Sinus Rhythm or Atrial Tachycardia, after CFGA and PVI (without cardioversion)

2. **Procedural Success**: Conversion of Atrial Fibrillation to Normal Sinus Rhythm or Atrial Tachycardia after overall ablation procedure, with or without the need for cardioversion
3. **Acute Success Post-CFGA**: Rate of conversion of Atrial Fibrillation to Normal Sinus Rhythm or Atrial Tachycardia, after CFGA only (before PVI and without cardioversion)
4. Incidence of confirmed entrance block post-PVI after adenosine/isoproterenol challenge
5. Freedom from documented symptomatic AF/AT/AFL recurrence (episodes \geq 30 seconds on an arrhythmia monitoring device) post the 3-month blanking period through the 12-month follow up.
6. Change of intra-cycle length from pre-CFGA to post-CFGA and post-PVI

The number and percentages of subjects with effectiveness endpoints (#1- #5) and the corresponding two-sided 95% binomial confidence intervals will be presented.

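### The two 12-month SAE percentages use a Safety Population that includes subjects who leave at Day 7 by design, so they are biased or ambiguous, depending on how those exits are counted

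*SAP*

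**What the plan says.** SAP 5.1 and Protocol 4.1 list four safety endpoints. Two are tied to 12 months: the incidence of all SAEs, and that of device- and procedure-related SAEs.

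SAP 10.4 (Safety) gives the measure: "Incidence of (S)AEs during the 12 month follow-up will be reported as the number of (S)AEs and the number of subjects experiencing (S)AEs". It continues: "The number and percentage of subjects with (S)AEs will be summarized overall and by AE type, seriousness, severity, relationship to device and procedure". The population follows: "The SP will be used as the analysis population". Protocol 15.3.1 agrees. SAP 6 and 10.1 add two-sided exact 95% intervals.

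SAP 7 puts every enrolled subject with the catheter inserted in the SP, "regardless if CARTOFINDER guided ablation was performed". Those without CARTOFINDER guided ablation (CFGA) have short follow-up. Under Protocol 6.4, when no target is found, "the subject will be treated per standard of care and exits the study after 7 day follow up". SAP 2 says such subjects will "be followed up 7 days after the ablation procedure". Protocol 11 and SAP 10.2 set the same 7 days for mapping failures and discontinued subjects, and extend it only to follow an SAE already reported.

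SAP 10.1 and 10.4 restrict percentages to subjects with non-missing outcomes, and SAP 10.6 rules out imputation. Neither document says what a missing outcome is for an SAE endpoint. No Kaplan-Meier, person-time or censoring rule is given for SAEs.

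**The concern.** The rate is labelled 12-month, but part of its denominator is never scheduled to be seen after Day 7. An event-free exit counts as a full 12-month non-event in both the percentage and the exact interval. The SAP avoids this elsewhere: 12-month freedom from recurrence, AAD use and repeat ablation are analysed in the Evaluable Population (EP, the CFGA subjects), with its eligible subset added for recurrence. Only the 12-month SAE rates mix the two follow-up lengths.

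Preliminary estimates of safety are one of the two stated aims of the sample size (SAP 8). As written, two analysts could follow the plan and report different 12-month SAE rates from the same data.

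**Working it through.** **Inputs.** From the documents: 12-month endpoints, SP denominator, 7-day exits, 40-70 evaluable subjects and exact 95% intervals. The plan has no SAE rate, exit share or power calculation to reproduce, so all event rates below are assumptions.

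**Size if exits stay in the denominator.** Let e be the exit share of the SP, Rx the exits' own 12-month risk of at least one SAE, and rx their risk by Day 7.

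Expected crude SP percentage − true SP 12-month risk = −e × (Rx − rx)

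This is never positive, and it does not require exits to resemble CFGA subjects. Understatement in percentage points:

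| Assumed risk (Day 7 → 12 months) | e = 5% | 10% | 20% | 30% |
|---|---|---|---|---|
| All SAEs, 10% → 20% | 0.5 | 1.0 | 2.0 | 3.0 |
| All SAEs, 5% → 20% | 0.75 | 1.5 | 3.0 | 4.5 |
| Related SAEs, 6% → 8% | 0.1 | 0.2 | 0.4 | 0.6 |

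For example, 0.20 × (0.20 − 0.10) = 2.0 points. If Rx = rx the error is zero.

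**Three readings of one dataset.** Take 40 CFGA subjects, 8 with an SAE, plus 10 exits, 1 with an SAE. The larger case has 70 CFGA subjects (14 with an SAE) plus 18 exits (2 with an SAE).

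| Reading | 40 + 10 | 70 + 18 |
|---|---|---|
| All exits kept | 9/50 = 18.0% | 16/88 = 18.2% |
| All exits dropped as missing | 8/40 = 20.0% | 14/70 = 20.0% |
| Only event-free exits dropped | 9/41 = 22.0% | 16/72 = 22.2% |

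The second reading is the EP rate and loses the exits' early SAEs. The third overstates, because it keeps exits only when they have had an event.

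**Censoring at Day 7.** Suppose 4 of the 8 CFGA events fall by Day 7. Then 5 of 50 have an event by Day 7, and 4 of the remaining 36 CFGA subjects have one later. Kaplan-Meier gives 1 − (45/50) × (32/36) = 20.0%, against 18.0% crude.

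**Precision.** The exact 95% interval is 9.1-35.6% for 8/40 (half-width about 13 points) and 11.4-31.3% for 14/70 (about 10 points). The interval for 9/50, 8.6-31.4%, treats all 50 as 12-month observations. The 10 exits supply 10 × 7 / (40 × 365 + 10 × 7) = 70/14,670 = 0.5% of planned follow-up days.

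**Direction against the CFGA-only rate.** Take 40 CFGA subjects with 6 SAEs, 2 of them by Day 7. With 10 exits and no SAEs, crude is 6/50 = 12.0%, EP is 6/40 = 15.0%, and Kaplan-Meier is 1 − (48/50) × (34/38) = 14.1%. With 3 SAEs among the exits, crude is 9/50 = 18.0%, EP is still 15.0%, and Kaplan-Meier is 1 − (45/50) × (34/38) = 19.5%. Crude is below Kaplan-Meier in both cases, but it can fall on either side of the EP rate.

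**Late primary events.** PV stenosis and atrio-esophageal fistula count as primary events beyond Day 7 in the same SP. With none observed, the exact upper limit is 7.1% if 50 are counted, and 8.8% for the 40 followed beyond Day 7, if all 40 are followed.

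**The case against.** The strongest case is that this is a descriptive feasibility study, that the SP is the usual safety population, and that the error is small beside the interval. The exit share may also be low: inclusion criterion 5 asks for enough left atrial activity to identify targets, and subjects found not in AF before insertion never enter the SP. SAE listings and disposition are planned, and split by CFGA status they would let a reader derive the EP proportion. All of this stands and limits the size. It does not supply a denominator rule or make the stated interval a 12-month one.

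The missing-outcome rule might be said to remove the exits already. It is undefined for SAEs, and either way of applying it has its own fault. Nor can the text settle the ordinary reading. An exit who attends the last scheduled visit arguably meets the Completed definition in SAP 10.2, but that section has separate categories for mapping failures and discontinued subjects, and disposition labels do not define missing outcomes. The separate table shells may state the denominator, but they cannot add follow-up that was not planned.

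Protocol 7.4 collects 3-, 6- and 12-month data for all subjects. The specific 7-day exit rules recur in both documents and are taken here as the design.

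A reader might infer that poorer mapping, by producing more exits, lowers the reported SAE rate. The documents do not support this. It needs the exits' 7-day risk to be below the CFGA subjects' 12-month risk, and it could be higher if a complication after insertion is what prevented CFGA.

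**Conclusion.** The concern holds as a fault in the planned denominator. With exits kept, the crude percentage understates the SP's own 12-month SAE risk whenever there are exits and some of their first SAEs fall after Day 7. The range is about 0.1 to 4.5 points for exit shares of 5-30% under the assumed risks, with related SAEs at the low end (0.1 to 0.6), against an interval half-width of about 10 to 13 points. Because the missing-outcome rule is undefined, the rate could instead be overstated or lose early events, so the direction is firm only for the ordinary reading.

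It would go too far to say that the existing data can remove the error. Exits' SAEs after Day 7 are not observed under the plan, so any 12-month figure for the whole SP rests on an assumption about them. The 0.5% share of follow-up days shows how little the exits can inform a 12-month rate. It does not measure bias, which is small if SAEs cluster around the procedure. The point should be fixed before analysis, and it does not threaten the study.

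**What to change.** In SAP 10.4 and Protocol 15.3.1:

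1. Report Day 0-7 SAEs and primary adverse events as percentages of the full SP.
2. Report 12-month all-SAE and related-SAE incidence by Kaplan-Meier in the SP, with Day-7 exits and dropouts censored at last contact. State that beyond Day 7 the estimate rests on CFGA subjects and assumes exits have similar later risk. Give the EP 12-month rate beside it. The EP rate alone would change the population and take exits' early SAEs out of the 12-month figure.
3. List the SAEs of Day-7 exits separately. Give the number followed beyond Day 7 for the 12-month SAE rates and for late PV stenosis and atrio-esophageal fistula.
4. If the crude SP percentage is kept, label it supportive, state its denominator, and state that event-free Day-7 exits are not missing but were observed for 7 days only.

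The cost is SAP and protocol wording and one extra table. Event dates, study day and an end-of-study page for all enrolled subjects are already planned. On the same data the Kaplan-Meier figure will not be below the crude SP percentage, and the EP rate may be higher or lower than it.

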7.2 Post-Procedure/Discharge

Once the investigator has achieved the desired results for the subject's arrhythmia, the subject will be monitored as per the institution standard of care (post procedure practice) and subject will be discharged from the hospital in accordance with the hospitals standard procedures.

The following data will be collected at Discharge:

- Arrhythmia assessment
- Adverse Events Procedural complication collection and notification
- Electrocardiogram (12-Lead ECG and cycle length in diagnosed rhythm)
- Cardiovascular medication and anti-coagulation therapy.

7.3 7-Day Follow-Up (Clinic Visit or telephone visit)

All subjects will be contacted 7-days post procedure via telephone or by attending a clinic visit.

The following data will be collected for all subjects at 7 days post- procedure:

- Arrhythmia assessment
- Medical/hospitalization assessment
- Concomitant cardio-vascular medication and anti-coagulation therapy
- Adverse event assessment and notification

7.4 3, 6 and -12 Months Follow-Up (Clinic Visit)

The following data will be collected for all subjects:

- Medical / Hospitalization assessment
- Arrhythmia assessment
- Electrocardiogram (12-Lead ECG and cycle length in diagnosed rhythm)
- Arrhythmia Monitoring:
 - 24-hour Holter at 3 month visits
 - ≥72 hours Holter at 6 and 12 months
- Concomitant cardiovascular medication and anti-coagulation therapy: subjects are recommended to stop their AAD medication after 3- months at the discretion of the investigator
- Adverse event assessment and notification

Repeat ablations may be performed at the discretion of the investigator. Investigators are recommended to treat the subject using the same commercial available ablation catheter (THERMOCOOL® SMARTTOUCH™ Catheter and/or SMARTTOUCH® SF Catheter) as the initial procedure. The follow-up schedule will remain based on the initial procedure.

Table 7.4 Time and Follow-up Schedule

	Screening / Baseline	Ablation Procedure ¹	Discharge	7 Days +/- 2 day	3 Month +/- 1 wks.	6 Month +/- 2 wks.	12 Month +/- 4 wks.
Informed consent ¹	X						
Inclusion & exclusion criteria	X						
Demographics	X						
Medical assessment	X [history]			X	X	X	X
Arrhythmias	X [history]		X	X	X	X	X
ECG (12 lead and CL measurement)	X		X		X	X	X
NYHA/CHADS-VASC2 score	X						
Pregnancy Test ²	X						
Assessment LA Thrombus ³		X					
TTE ⁴	X						
Ablation assessments		X					
Arrhythmia Monitoring (Holter) ⁸					X	X	X
Device Deficiency		X					

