9 HOLTER MONITOR

All subjects will be provided with a Holter monitor device at pre-specified scheduled visits (refer to Table 7.4) to capture recordings of their heart rhythm status and will be asked to report on any symptoms they experience. The recordings from the Holter monitor will be transmitted to a Core Lab for analysis. Subjects will be trained by the study site personnel on the use of the Holter monitor device and transmission of the recordings. A study specific Core Lab instruction manual and patient

instruction sheet, including procedures to be followed, will be made available.

Holter monitoring will be conducted as follows:

- 3-Month Visit: 24-hour Holter Monitor
- 6 and 12 Month Visits: \geq 72 hours Holter Monitor

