20 ATTACHMENTS

20.1 Attachment A: Definitions

Term	Definition
Adverse Event (AE)	
Any unfavorable and unintended sign, medical occurrence, disease or injury (including abnormal laboratory findings) in subjects, users or other persons temporally associated with the use of a medicinal product or device (investigational) whether or not related to the investigational product.
 
This definition includes events related to the investigational medical device and/or the comparator, and events related to the procedure in which the investigational device was used.

Adverse Device Effects (ADE's)	
Adverse events related to the use of an investigational medical device. This definition includes adverse events resulting from insufficient or inadequate instructions for use deployment, implantation, installation, or operation, or any malfunction of the investigational medical device. This definition includes any event resulting from use errors or from intentional misuse of the investigation medical device.

AF Episode	
An atrial fibrillation episode is defined as AF which is documented by ECG monitoring and has a duration of at least 30 seconds, or if less than 30 seconds, is present continuously throughout the ECG monitoring tracing. The presence of subsequent episodes of AF requires that sinus rhythm be documented by ECG monitoring between AF episodes

Anticipated AE	
An effect which by its nature, incidence, severity or outcome has been identified as possible complications associated with the investigational medical device and/ or intervention procedure.

Atypical Flutter	
Macroreentrant circuits within the atria where activation rotates around large obstacles that does not meet the criteria for Typical Flutter.

Baseline Rate	
Is the recorded rate from the subject demonstrating the ventricular response of the subjects arrhythmia.

Term	Definition
Cycle Length Measurement	Cycle Length will be measured by placing a multielectrode catheter (connected to the recording system) in the CS calculating the average CL over 10 repetitive cycles.
Device Deficiency	Inadequacy of a medical device related to its identity, quality, durability, reliability, safety or performance, such as malfunction (failure of a medical device to perform in accordance with its intended purpose when used in accordance with the instructions for use or protocol), misuse or use error and inadequate labeling.

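### As worded in the SAP, 12-month freedom does not count symptomatic AF documented only on a 12-lead ECG shorter than 30 seconds, and the protocol's own wordings disagree on whether it should

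*SAP*

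**What the plan says.** SAP 10.4, outcome 5, is "Freedom from documented symptomatic AF/AT/AFL recurrence", with episodes of at least "30 seconds on an arrhythmia monitoring device) post the 3-month blanking period through the 12-month follow up". The Protocol Synopsis, Protocol 4.1 and SAP 5.1 carry the same conditions.

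Protocol Attachment A defines an AF episode more widely. It needs a "duration of at least 30 seconds, or if less than 30 seconds, is present continuously throughout the ECG monitoring tracing".

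Protocol 15.3.2, which describes the effectiveness analysis, words the same endpoint without requiring symptoms, a minimum duration or a device.

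Neither document defines an arrhythmia monitoring device. The SAP schedule (section 4, matching Protocol Table 7.4) has one row beginning "Arrhythmia Monitoring (Holter" and a separate row beginning "ECG (12 lead and CL measurement". Protocol 7.4 lists, for the 3-, 6- and 12-month visits, an "Electrocardiogram (12-Lead ECG and cycle length in diagnosed rhythm"), and separately a 24-hour Holter at 3 months and a Holter of at least 72 hours at 6 and 12 months. Protocol 9 sends Holter recordings to a Core Lab and says nothing comparable about ECGs.

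SAP 10.4 leaves subjects with missing outcomes out of each endpoint analysis, and SAP 10.6 rules out imputation.

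**The concern.** The trial enrols persistent AF, so a patient who presents in AF on an ECG is an expected form of failure. The sites collect that evidence through the scheduled ECGs, the arrhythmia assessment at each visit, and any ECG taken when a symptomatic patient attends between visits. No rule says how it enters the 12-month endpoint.

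Read literally, the SAP leaves it out unless a Holter also shows the arrhythmia. A subject with symptomatic AF on an ECG and a clean Holter is scored as free. One with no usable Holter is scored as free or removed as missing. The error runs one way, towards a higher freedom rate.

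No other outcome clearly recovers these cases. Protocol 14.3 says that recurrence of the study arrhythmia is not in itself an adverse event, and the repeat-ablation assessment misses recurrences managed without ablation. Because the endpoint is worded differently within the protocol, someone must also choose between the wordings, possibly with the data in view, in an open-label single-arm study.

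**Working it through.** The plan states no figure that depends on this definition, so there is none to reproduce. The check compares the wordings and then scales the effect.

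**Step 1: one case under each wording.** Take symptomatic AF after Day 90, present throughout a 12-lead ECG shorter than 30 seconds, with no Holter evidence.

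- Synopsis, Protocol 4.1, SAP 5.1, SAP 10.4: not a recurrence.
- Attachment A: an AF episode, provided that a 12-lead ECG is an ECG monitoring tracing.
- Protocol 15.3.2: a recurrence.

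**Step 2: does this depend on how monitoring is read?**

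- Narrow reading (Holter only, throughout): the ECG is not an endpoint device, so the case fails SAP 10.4 whatever the tracing length. Attachment A is then silent, and the conflict is with Protocol 15.3.2.
- Wide reading (12-lead ECG included, throughout): the case still fails SAP 10.4 because the tracing is under 30 seconds, while Attachment A counts it.
- The conflict disappears only if the 12-lead ECG is a monitoring device and the tracing lasts at least 30 seconds. The documents state neither.

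**Step 3: where it can change a result.** The 3-month visit, with its "3-Month Visit: 24-hour Holter Monitor", has a window of one week either side and so straddles the end of blanking at Day 90. The ECGs that matter are mainly those at 6 and 12 months and any taken between visits. AF that is still sustained at 6 or 12 months would usually also appear on the Holter of at least 72 hours due at that visit. That leaves missing or unreadable Holters, and AF documented and terminated between Holters.

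**Step 4: scale per subject.** Inputs: N = 40 and 70 evaluable subjects (Protocol 15.1, SAP 8) and exact binomial intervals (SAP 10.1). A 60% freedom rate is assumed for illustration; it is the top of the 40% to 60% one-procedure success range in Protocol 2.1.

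Moving k subjects from free to failed changes the estimate by k/N: 1/40 = 2.5 points and 1/70 = 1.4 points per subject.

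- N=40: 24/40 = 60.0% (95% CI 43.3 to 75.1); k=1, 23/40 = 57.5% (40.9 to 73.0); k=2, 22/40 = 55.0% (38.5 to 70.7).
- N=70: 42/70 = 60.0% (47.6 to 71.5); k=1, 41/70 = 58.6% (46.2 to 70.2); k=2, 40/70 = 57.1% (44.7 to 68.9).

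The values of k are illustrative.

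**Step 5: direction when the subject is excluded instead.** With F subjects free, dropping one failure changes F/N to F/(N−1), which is always higher.

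- True rate 60%: 24/39 = 61.5% (up 1.5 points); 42/69 = 60.9% (up 0.9).
- True rate 40%: 16/39 = 41.0% (up 1.0); 28/69 = 40.6% (up 0.6).

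Exclusion biases in the same direction as scoring the subject free, by less.

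**The case against.** **The device is undefined.** Rows in a visit schedule organise assessments and do not define an endpoint, and the ECG length is not stated. This stands. It makes the Holter-only reading the most natural one, not a certain one. Step 2 shows that the gap survives either consistent reading of monitoring unless the ECG is a device and also runs to 30 seconds.

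**Attachment A does not name the 12-lead ECG and covers AF only.** This stands too. The definition cannot be applied to AT or AFL without saying so.

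**Protocol 15.3.2 may be shorthand.** Possibly, but it sits in the analysis section and nothing there refers back to the fuller wording.

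**Most sustained AF would be caught anyway.** Correct, and it limits the effect to the situations in Step 3. A reader might infer that every AF tracing on a scheduled ECG is lost to the endpoint. The documents do not support that.

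**A large bias is not shown.** A reader might note that two 72-hour Holters cover 144 of the 6,600 hours in Day 91 to 365 (275 × 24), or 2.2%, and infer that freedom is overstated by many points. That does not follow. Brief ECGs add almost no recording time, and low coverage is a separate matter of intermittent AF. The documents give no share of failures seen only on ECG. The symptom condition would also still exclude asymptomatic ECG findings after the fix.

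**The study is a feasibility study.** There is no hypothesis test, and the 95% interval half-widths at 60% are about 16 points at N=40 and 12 at N=70. One or two subjects would not change the broad picture.

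**Conclusion.** The point holds as a conflict of definitions with a one-directional effect. Under the SAP wording, symptomatic AF documented only on a 12-lead ECG shorter than 30 seconds is not a recurrence; under Protocol 15.3.2 it is, and Attachment A supports counting it. A known failure can therefore be reported as free or left out, and both raise the freedom rate.

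The conclusion assumes that the tracing is shorter than 30 seconds or that the 12-lead ECG is not a monitoring device. Its total size is unknown, because the number of ECG-only cases cannot be derived from the documents. What can be stated is the effect per reclassified subject given in Step 4. It should be corrected, because the endpoint should not be open to two answers for the same patient, but the documents do not show that the freedom estimate would be seriously distorted.

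**What to change.** Use one recurrence definition in the Protocol Synopsis, Protocol 4.1, Protocol 15.3.2, SAP 5.1 and SAP 10.4: symptomatic AF, AT or AFL after blanking that either lasts at least 30 seconds on a monitoring device or is present throughout a 12-lead ECG tracing. Say explicitly that the second limb takes the Attachment A rule and extends it to AT and AFL.

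State also that:

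- scheduled ECGs count, as does any unscheduled ECG already documented by the site;
- the site's rhythm diagnosis and the symptoms recorded at that contact are used;
- a subject with such an ECG is a failure even if the Holter is missing.

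The cost is small. No visit or test is added, and treatment is unaffected. The protocol wording has to go through the amendment route in Protocol 16.3, and the SAP needs a revision. There are two drawbacks: the freedom rate may be slightly less favourable, and ECG-only events would be read by the site, not by the Core Lab.
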